## FOLLOW-UP FORM 1/3

### SECTION 2 – FOLLOW-UP

The follow-up is intended for up to 2 years, with total maximum 8 contacts plus unpredictable number of unplanned contacts (few).

#### Interview ID

ID (from system) .....	_ _ _ _ _ _ _	[obtained from database based on username/password and number within center]
Nominal contact time (month):  _ _  [options: 3-6-9-12-15-18-21-24 plus 9# (starting from 90 and increased by 1 at each new unplanned visit: unplanned proposed by system, can be replaced. CHECK: baseline must be present; conclusion must not be present. Investigator informed forty days in advance by mail. If not completed within 2 weeks from due date, new mail to the investigator. For visits 12-and 24 the mail should indicate that a visit at the center should be planned.]		
Date of contact (dd/mm/yyyy):  _ _ / _ _ / _ _ _ _		
Type of contact:	 1=telephone call; 2=visit at center	if type=2: Type of visit:  1=planned by investigator 2=planned, requested by patient 3=unplanned

## Events occurred after last interview

[check: if any left box is marked "yes", there MUST be a right box marked "yes" or date/reason]

Thrombotic complications:	 0-no	if yes, specify:	deep vein thrombosis pulmonary embolism superficial vein thrombosis transient ischemic attack (TIA) ischemic stroke acute myocardial infarction sudden/cardiac death other; specify	 0-no; 1-yes; default=no        [CHECK death below]
[text]				
Bleeding complications:	 0-no; 1-yes; default=no	
 _ _  0; if bleeding complication=yes, should be <math>\geq 1</math>
 
 major bleeding  clinically relevant non-major bleeding  other bleeding
 
N/A; if bleeding complication = yes, at least one should be indicated
 
HELP BOX BLEEDING CLASSIFICATION
		
if yes, specify how many:				
if yes, specify:		type of complication:		

if yes, specify the nature of the complication:
 
cerebral hemorrhage/hemorrhagic stroke gastrointestinal hemorrhage retroperitoneal hemorrhage intra-ocular hemorrhage retinal bleeding intra-articular hemorrhage (hemarthrosis) hemoglobin drop by 2 or more g/dL transfusion of 2 or more units of red cell concentrate uterine bleeding skin/muscle hematoma nose bleed bleeding gums anal bleeding other; specify
				
[text]				
Hospitalization:	 0-no  1-yes	if yes, specify:	date (dd/mm/yyyy)  _ _ / _ _ / _ _ _ _	[text]
Patient's death:	 0-no  1-yes	if yes, specify:	date (dd/mm/yyyy)  _ _ / _ _ / _ _ _ _	
Any other event preventing continuation of the follow-up	 0-no  1-yes	if yes, specify:	date (dd/mm/yyyy)  _ _ / _ _ / _ _ _ _	[text]
		reason:	_ _ _ _ _ _ _ _ _ _	

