Main objective of the study	
This study includes two sections:
 
 
a] a transversal section, in which the primary objective will be evaluated;
 
b] a longitudinal section, in which the secondary objectives will be evaluated.
 
 
It is assumed that the distribution of the decision taken during the transversal section (primary objective) may influence the outcomes of the longitudinal section.
 
The primary objective of the study is the evaluation of the distribution of decisions and of the reasons guiding the physician's decision on the modality to manage the secondary prevention of venous thromboembolism (VTE) in patients treated for a first-ever episode of VTE, after the initial 3-12 months of anticoagulation therapy.
 
The secondary objective is the collection of data on the course of VTE recurrence, bleeding and death risk.

Endpoints of the study	
Primary endpoint:
 
The primary endpoint is the decision taken by the attending physician at the end of the period of maintenance anticoagulation (from the end of the 3rd month to the end 12th month) initiated after the index event (maintenance anticoagulation). The maintenance anticoagulant used may or may not be the same used in the acute phase of DVT (initial 7 days); for the objectives of this study, the acute treatment is not of interest. The primary endpoint will be evaluated at the visit performed at the end of the maintenance anticoagulation.
 
Secondary endpoints
 
The distribution of reasons guiding the physician's decision on the modality to manage the secondary prevention of VTE represents a secondary endpoint.
 
The other secondary endpoints encompass the frequency of thromboembolic complications, of bleeding complications, or death from any cause monitored during the follow-up.

Number of Countries	Nine: Portugal, Poland, Czech Republic, Slovakia, Rumania, Russia, Tunisia, China, Mexico
Number of Centers	Approximately from 5 to 20 Centers in each Country. Each center shall recruit not more than 40 subjects.

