#### 8.1.2 Secondary endpoints

The secondary endpoints include:

- the distribution of the reasons that were considered relevant by the attending physician to take the decision indicated as primary endpoint;
- the rate of thromboembolic complications and the combined rate of bleeding requiring at least an interview with the attending physician (major or clinically relevant non-major bleeding), or death from any cause during the 2-year follow-up.

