### 10.2 Sample size

The study anticipates recruiting approximately 3,200 subjects, based on considerations relevant to the primary endpoint.

The primary endpoint is the decision taken by the attending physician at the end of the maintenance anticoagulation initiated after the index event. Three options are possible: continue with extended anticoagulation (regardless of individual drug and dose), replace the anticoagulation with an antithrombotic, non-anticoagulant treatment, or stop any pharmacological prophylactic treatment.

In absence of other determinants, the null hypothesis is that the distribution of subjects by option is uniform. The analysis can therefore be performed with a goodness-of-fit test with 2 degrees of freedom. The alternative hypothesis is that at least one of the three choices is selected in a greater proportion than the other two. This analysis is performed once only at the end of recruitment.

With approximately 3,200 subjects, the study has 90% power to detect with 95% confidence a deviation from the uniform distribution, in case one of the options is selected in a proportion exceeding by 10% relative or more the proportion expected from the uniform distribution (i.e., in 36.3% or more of the subjects) [7].

Given that the factor “country” (synonymous of “healthcare system”) will be a likely cofactor in the analyses, the sample should be split across the participating countries in such a way to allow a reliable representativeness also for the smaller countries. The limit was considered not less than 100 subjects per country. The anticipated contribution by country was therefore estimated as:

Country	cases
China	approximately 200
Czechia	approximately 350
Mexico	approximately 300
Poland	approximately 900
Portugal	approximately 350
Romania	approximately 250
Russia	approximately 800
Slovakia	approximately 150
Tunisia	not less than 100

Since in this study the secondary endpoints are of clinical relevance as well, it is appropriate to estimate whether the indicated sample can yield reliable information also in relation to such endpoints.

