The secondary endpoints are the rate of thromboembolic complications and the combined rate of bleeding complications/death. To allow the DMSB (§ 11.3) to take appropriate decisions on the conduct of the study, these analyses will be performed at yearly intervals, i.e., when the last recruited subject has reached the end-of-year observation. There will therefore be 2 analyses (1 interim and one final), so that the final analysis will have to report as statistically relevant and deserving further investigations,  $P$ -values  $\leq 0.048$ .[8]

The interest of the study is to find whether any of the three constituted sub-populations – extended anticoagulation; long-term antithrombotic prophylaxis; no pharmacological prophylaxis (§ 8.1) – deviates from the expected risk, to an extent deserving investigation of the potential predictors of outcome.

From the literature [2, 3], the estimated annual risk of recurrence in the control group was approximately 5 events per 100 subject-years. The combined risk of bleeding or death was approximately 1 event per 100 subject-years.

Assuming that almost all recruited subjects will be monitored for at least one year, this survey has 80% power to detect with a two-tailed 95% confidence (after accounting for the interim analyses) a Cohen’s effect of the baseline decision taken on the follow-up outcomes, of 0.055 [9]. It can therefore identify as potentially relevant, deviations of at least one of the constituted sub-population from the anticipated recurrence rate of at least  $\pm 0.0123$  (3.77 or less, or 6.23 or more, events per 100 patients per year). Similarly, it has 80% power to detect with a two-tailed 95% confidence a deviation of at least one of the three constituted sub-populations from the anticipated bleeding/death rate of  $\pm 0.0055$  (0.45 or less, or 1.55 or more, events per 100 patients per year). [10]

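### The follow-up endpoint compared with a recurrence rate of 5 per 100 is listed on the CRF as a broader set of events than DVT and PE

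*Combined protocol and SAP*

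**What the plan says.** The synopsis states the follow-up aim in terms of venous recurrence: "The secondary objective is the collection of data on the course of VTE recurrence, bleeding and death risk". Section 7.2.2 words the same aim more broadly, as thromboembolic complications. Section 8.1.2 names the endpoints as "the rate of thromboembolic complications and the combined rate of bleeding requiring at least an interview with the attending physician" (major or clinically relevant non-major), "or death from any cause during the 2-year follow-up". No section of the protocol text lists what a thromboembolic complication is.

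The benchmarks are in section 10.2: "the estimated annual risk of recurrence in the control group was approximately 5 events per 100 subject-years", and "The combined risk of bleeding or death was approximately 1 event per 100 subject-years". Section 10.4.3 then analyses deviations of the observed rates from the expected rates, with a final critical P value of 0.048.

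The only list of components is in Appendix IV, follow-up form, under events since the last interview. One yes/no field for thrombotic complications opens boxes for DVT, PE, "superficial vein thrombosis transient ischemic attack (TIA) ischemic stroke acute myocardial infarction sudden/cardiac death", and other. The decision box that closes the follow-up form sends any thrombotic complication to the end of the trial. The end-of-study form has a single thromboembolic-event entry, checked against the last follow-up form.

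**The concern.** A comparison with an external rate is meaningful only if numerator and benchmark count the same thing. Here the benchmark is a recurrence rate, while the field that supplies the numerator also takes in arterial events, superficial thrombosis, cardiac death and an open category. These extra events can push a sub-population above 5 per 100 with no excess of DVT/PE, or lift a low DVT/PE rate back to 5.

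The extra events need not be spread evenly. Treatment is chosen freely by the physician, the second option includes antiplatelet drugs (section 6.2), and the baseline form shows that ischemic heart disease and previous stroke will vary between patients. Arterial event rates could therefore differ between sub-populations while venous recurrence does not.

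The interim results on these endpoints go to the DMSB, which decides whether observation continues (section 10.4.3). In addition, because any thrombotic complication ends follow-up, a superficial thrombosis or TIA removes the patient from observation for a later DVT or PE.

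**Working it through.** **1. The plan's own figures.** Section 10.2 gives N of about 3,200, 80% power and a Cohen effect w = 0.055, with detectable limits of 3.77 and 6.23 around 5 per 100 and 0.45 and 1.55 around 1 per 100.

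- A noncentral chi-square with 2 degrees of freedom and noncentrality N·w² = 3,200 × 0.055² = 9.68 gives power 80.2% at alpha 0.05 and 79.7% at 0.048.
- The deviation is w·√p0: 0.055 × √0.05 = 0.0123, and 0.055 × √0.01 = 0.0055.

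The figures reproduce. The arithmetic is sound; the question is what is counted.

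**2. Inputs for the effect of the mismatch.**

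- Benchmark p0 = 0.05 (section 10.2), taken to mean DVT/PE recurrence.
- Two-sided critical P value 0.048 (sections 10.2, 10.4.3 and 11.3), z = 1.977. The synopsis gives 0.03 instead; I used the value in the body of the protocol.
- Sub-population size n: not given. Assumed 1,067 (one third of 3,200), with 640 (20%) as a smaller case.
- Rate x of events in the CRF field that are not DVT/PE: not given. Assumed 0.25 to 2.0 per 100 per year, plus 1.23, the plan's own detectable deviation.
- One year per subject, so that a rate per 100 can be treated as a proportion.

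**3. Chance of a flag when DVT/PE is exactly at benchmark.** This is a one-sample normal test. For n = 1,067, SE0 = √(0.05 × 0.95 / 1,067) = 0.00667, so a result is flagged above 5 + 1.977 × 0.667 = 6.32 or below 3.68 per 100. The observed rate is centred on p1 = 0.05 + x, with SE1 = √(p1(1 − p1)/n).

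For x = 1.0 per 100: SE1 = √(0.06 × 0.94 / 1,067) = 0.00727. Then (0.0632 − 0.06)/0.00727 = 0.44, an upper tail of 33.0%; the lower tail adds 0.1%, giving 33.1%.

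| Added events per 100 per year (assumed) | n = 1,067 | n = 640 |
|---|---|---|
| 0 | 4.8% | 4.8% |
| 0.25 | 6.9% | 6.3% |
| 0.5 | 12.5% | 9.8% |
| 1.0 | 33.1% | 22.9% |
| 1.23 | 45.2% | 31.1% |
| 2.0 | 80.8% | 61.6% |

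**4. Masking.** Take a true DVT/PE rate of 3.77, the plan's lower detectable limit. With n = 1,067 the chance of flagging it as low is 43.9% with nothing added, 17.1% with 0.5 added and 4.8% with 1.0 added. With 1.23 added the expected reading is 3.77 + 1.23 = 5.00, and the deviation vanishes.

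These are single-group illustrations. The plan's 80% power rests on the full 3,200 and 2 degrees of freedom, so the percentages show direction and order of size, not the operating characteristics of the planned test.

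**The case against.** **The CRF is a collection form, not an endpoint definition.** Each component has its own box, and no sentence says that every box counts against 5 per 100. This stands in part: the pooling is a reading of the form, not a stated rule. But nothing in the plan selects among the boxes, and both the end-of-trial rule and the end-of-study check treat the field as one event.

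**A broad endpoint may be intended.** Section 7.2.2 and the endpoint wording speak of thromboembolic complications; only the synopsis objective says VTE recurrence. That is fair, but a deliberately broad endpoint would need a broad benchmark, and the one given is a recurrence rate.

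**The stakes are limited.** Analyses are described as descriptive and exploratory (section 10.1), the sample size comes from the primary endpoint, and the Steering Committee resolves doubtful outcome classifications without knowing the treatment (section 11.1). This tempers the consequence. It does not cure the mismatch, because the plan still tests against the benchmark at a stated P value, and case-by-case classification does not define components.

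Three stronger readings are tempting, and the documents do not support them:

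- *That 6.23 per 100 is a trigger.* It is the deviation detectable with 80% power; results are flagged by P value. An added 1.23 per 100 would be flagged about 45% of the time with n = 1,067.
- *That cardiac death is double counted.* A sudden or cardiac death can appear in both endpoints, as can a fatal PE or stroke, but the two are reported separately and never summed. The overlap makes them non-independent and nothing more.
- *That cardiac deaths inflate the bleeding/death endpoint against its benchmark of 1 per 100.* That endpoint includes death from any cause and its benchmark is a combined bleeding-or-death risk, so cardiac deaths belong there by definition.

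**Conclusion.** The concern holds as a mismatch between endpoint and benchmark. The rate of 5 per 100 describes recurrence; the endpoint compared with it has no components defined in the text, and its only operational list is wider than DVT/PE. Followed as written, the plan compares unlike quantities, and the error can run in either direction.

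Its size depends on two figures that the documents do not give: the sub-population size and the rate of the additional events. It is small if those events are rare (6.9% against a nominal 4.8% at 0.25 per 100, n = 1,067) and serious if they reach 1 to 2 per 100. The conclusion also assumes that the benchmark means DVT/PE; the cited sources were not available to confirm this. The sample size and the stated detectable limits are unaffected if the tested endpoint is DVT/PE only.

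**What to change.** - In sections 10.2 and 10.4.3, define the endpoint compared with 5 per 100 as DVT and/or PE, including fatal PE, derived from the existing separate CRF boxes. Do not restrict it to the lower limbs: the follow-up form records no DVT site, so that restriction could not be derived.
- Report superficial vein thrombosis and the arterial events separately, by sub-population, outside the benchmark comparison, and say how the open category is assigned.
- State that sudden/cardiac death counts in the bleeding/death endpoint and is a competing event for DVT/PE.
- Since any thrombotic complication ends follow-up, state whether an earlier non-DVT/PE event is a competing or a censoring event in the DVT/PE analysis, and report how many subjects left observation this way in each sub-population. A definition alone cannot recover DVT/PE occurring after such an exit.
- Reconcile the wording of the synopsis objective, sections 7.2.2, 8.1.2 and 10.2, the follow-up form and its end-of-trial rule.

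The cost is a few sentences, settled before event data are analysed, with no new data item. The one downside is fewer events in the tested endpoint.

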## HELP BOX BLEEDING

1. A major bleeding is defined as having a symptomatic presentation and:
  - is fatal, and/or
  - occurs in a critical area or organ, such as intracranial, intraspinal, intraocular, retroperitoneal, intraarticular or pericardial, or intramuscular with compartment syndrome, and/or
  - causes a fall in hemoglobin level of 20 g/L (1.24 mmol/L) or more, or leads to transfusion of two or more units of whole blood or red cells.
- 2 A clinically relevant non-major bleeding is defined as any sign or symptom of hemorrhage (e.g., more bleeding than would be expected for a clinical circumstance, including bleeding found by imaging alone) that does not fit the criteria for the definition of major bleeding above, but does meet at least one of the following criteria:
  - requiring medical intervention by a healthcare professional;
  - leading to hospitalization or increased level of care;
  - prompting a face to face (i.e., not just a telephone or electronic communication) evaluation.
3. All bleedings that do not meet definition 1 or definition 2 are classified as “other”.

*Reference:* Kaatz S, Ahmad D, Spyropoulos AC, Schulman S, for the Subcommittee on Control of Anticoagulation. Definition of clinically relevant non-major bleeding in studies of anticoagulants in atrial fibrillation and venous thromboembolic disease in non-surgical patients: communication from the SSC of the ISTH. *J Thromb Haemost* 2015; **13**: 2119–26.

## Antithromboembolic therapy

There was any change in the prescribed anti-thromboembolic therapy after the last contact (in the last 3/6 months)?  0-no; 1-yes

If yes, the therapy was:  dose reduced (not discontinued): 1

dose increased: 2

newly instituted: 3

discontinued without replacement: 4

replaced with another therapy: 5

[if change=0, blank; if change=1 MUST be filled;

if replaced, continue with boxes below]

Specify if change was decided by:  investigator or co-investigator

other physician

spontaneously by patient

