	
study, which is observational, it is not designed to confirm or reject predetermined hypotheses.
 
Populations
 
The analyses will be performed on the total sample monitored. Missing data will not be replaced.
 
Demographic, prognostic and descriptive variables
 
All variables will be summarized with the usual descriptive techniques: categorical variables as contingency table (absolute and relative frequency); continuous variables with sampling statistics: mean, standard deviation, median, minimum, maximum. Whenever appropriate the relevant 95% confidence interval will also be reported.
 
Primary endpoint
 
The primary endpoint will be analyzed at the completion of the recruitment. The proportion of choices made by the attending physician will be reported as proportion with confidence interval by level. The primary analysis will test by goodness-of-fit whether the choices were random or not. The impact of demographic and prognostic factors – including country – on the choice can be tested by chi square and/or logistic regression analysis.
 
Secondary endpoints
 
Frequency of thromboembolic complications and frequency of bleeding complications or death for any reason will be analyzed at the completion of each year of observation. The interim results will be used by the DMSB to decide on whether the observation has to continue or must be stopped. The final analysis will be adjusted for multiplicity using the nominal critical P value of 0.03.
 
Event rates will be reported at the available observations, stratified by sub-population, as proportion with the relevant confidence interval. Proportions will be compared if appropriate by chi square and/or as time to event by survival analysis.
 
Since clinically-relevant non-major bleeding may not be a reason for interrupting the follow-up, and minor bleeding are not a reason for interruption, it is possible that the number of bleeding events per subject can be submitted to analysis by Poisson regression.
 
The other secondary endpoint is the reason(s) justifying the choice analyzed as primary endpoint. These will be tabulated by choice and compared, if appropriate, by chi square test or by ordinal logistic regression. Unplanned post-hoc subgroup analyses may be performed if requested by the Steering Committee.
 
Other endpoints
 
Occurrence of hospitalization and changes of prophylactic therapy, including institution of a therapy in subjects who stopped any prophylactic treatment at recruitment; change of the prophylactic treatment assigned at recruitment, and interruption of the prophylactic treatment assigned at recruitment.
 
Hospitalizations will be analyzed as proportion of subjects with event, compared between sub-populations, if appropriate, by chi square or in case of an appreciable number of events, by Poisson regression.
 
Changes in therapy will be tabulated as absolute number and proportion stratified by sub-population and, if appropriate, analyzed by chi square and/or logistic regression. In addition, the reasons for study termination may be considered an endpoint. These will be tabulated by sub-population and compared, if appropriate, by chi square or ordinal logistic regression.
 
Safety observations
 
Adverse events will be handled by the attending physician according to the local procedures and, as in any observational study, will not be subject to statistical analysis. Only those events that resulted in the interruption of follow-up will be tabulated by sub-population and/or individual medication, without further statistical considerations.

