## **3. Unplanned follow-up visit**

Upon request of the subject, or by decision of the investigator based on the communications with the subject, there may be the need for unplanned follow-up interviews. This will usually occur when a thromboembolic complication or a bleeding complication or other events occurred, that make clinically relevant for the well-being of the subject a direct contact with the investigator.

The information to be collected at these visits is the same as that of the follow-up visit. Usually, these visits imply the conclusion of the follow-up on the individual subject.

The follow-up is to be concluded, filling the end-of-study form discussed below, when:

- a. a thromboembolic complication occurred;
- b. a major bleeding complication occurred. Clinically relevant non-major bleedings as well as minor bleedings do not automatically imply the interruption of the follow-up and the relevant decision will be taken by the investigator case by case on the best subject's interest;
- c. there was a substantial change in anti-thrombotic therapy, such as:
  - institution, by the investigator or another physician, of a prophylactic therapy in a subject for whom the decision was taken not to continue the pharmacological prophylaxis;
  - replacement, by the investigator or another physician, of the current therapy with a new therapy of another therapeutic class. Changes of dosage of the same therapy do not imply interruption of the follow-up;
  - interruption, by the investigator or another physician or by subject's spontaneous decision, of the prescribed prophylactic treatment;
- d. an event occurred, that implied the impossibility to continue a correct monitoring, e.g., a planned/unplanned intervention requiring prolonged anticoagulation (e.g., surgery or immobilization).

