##### *8.3.2 Variables*

The variables to be collected in this study are the usual descriptive, diagnostic and prognostic variables normally recorded in the subject's cards, as well as the description of the antithrombotic treatments applied and the reason for change. In the follow-up, the usual outcome variables relevant to the subject's status will also be collected.

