#### **10.4.5 Safety observations**

Being this an observational study in which any prescription is by free physician's choice in accordance with the drug's technical data sheet, all safety information will be handled by the attending physician according to the local procedures. Since, however, events may occur, which are not endpoints but may imply the termination of the follow-up, these events will be tabulated by sub-population and/or individual medication, without additional statistical considerations.

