#### Reason for concluding the follow-up of this patient

The patient reached the end of the planned observation period	 date:  _ _ / _ _ / _ _ _ _ _
	0-no; 1-yes; default=no exact date: dd/mm/yyyy
Showed a thromboembolic event	 date:  _ _ / _ _ / _ _ _ _ _
Showed a major bleeding event	 date:  _ _ / _ _ / _ _ _ _ _
Had a major change in therapy	 date:  _ _ _ _ _ / _ _ _ _ _
Reported another event preventing continuation of the follow-up	 date:  _ _ _ _ _ / _ _ _ _ _
	these dates may be incomplete (no day)
The patient died	 date:  _ _ / _ _ / _ _ _ _ _
The patient reported to another hospital	 date:  _ _ _ _ _ / _ _ _ _ _
The patient moved to another place	 date:  _ _ _ _ _ / _ _ _ _ _
The patient was lost to follow-up	 date:  _ _ _ _ _ / _ _ _ _ _

**CHECK:** at least one must be marked yes; if thromboembolic event is marked, there must be a thromboembolic event in the last follow-up form; if bleeding event is marked, there must be a bleeding event in the last follow-up form, items 1-9; if died is marked, there should be death=yes in last follow-up form, if other event is marked, there must be a "other event" marked in the last follow-up form.

After this form is concluded, the case is closed and cannot be modified by the users. It can be re-opened upon request (ticket), endorsed by the study supervisors.

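### The follow-up form records who changed the therapy but not why, so capture of drug-stopping adverse events for the planned safety table is optional and probably incomplete

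*Combined protocol and SAP*

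**What the plan says.** **The planned table.** Section 10.4.5 says of non-endpoint events that may end follow-up: "these events will be tabulated by sub-population and/or individual medication, without additional statistical considerations". The synopsis, under safety observations, limits this to adverse events that ended follow-up: "Only those events that resulted in the interruption of follow-up will be tabulated by sub-population and/or individual medication".

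**What ends follow-up.** Section 8.3.1 (unplanned follow-up visit) lists under item c, substantial change in therapy, the start of a drug in an untreated subject, replacement by another class, and "interruption, by the investigator or another physician or by subject's spontaneous decision, of the prescribed prophylactic treatment". Other events that prevent correct monitoring are a separate item d. Dosage changes are exempt. Section 10.4.4 makes institution, change and interruption of therapy monitored endpoints, to be tabulated by sub-population, and also tabulates the reasons for termination.

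**What the forms collect.** The therapy block of the follow-up form has five codes for the type of change, for example "discontinued without replacement: 4", and then "Specify if change was decided by" (investigator, other physician or patient). The drug boxes carry the instruction "if replaced, continue with boxes below". The end-of-study form offers "Had a major change in therapy" with a date.

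**The variable list.** Section 8.3.2 opens by naming "the description of the antithrombotic treatments applied and the reason for change" among the variables to be collected.

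**The concern.** In a subject on extended anticoagulation or on alternative prophylaxis, an intolerance or a non-bleeding adverse reaction will usually end follow-up because the drug is stopped or replaced. That is the route for which no cause is requested. In a subject without drug prophylaxis, a non-endpoint event that ends follow-up directly falls under the other-event line, which has a reason entry. The same class of event is thus likely to be recorded less completely in the treated groups, in a table meant to be read by sub-population and drug.

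The therapy-change endpoint of 10.4.4 is affected as well. A stop for harm, the end of a planned course (planned duration is recorded at baseline), a patient's preference and a cost decision all carry the same code. Because the change also closes observation for the analyses in 10.4.3, the missing cause removes information needed to judge whether that censoring is related to risk.

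**Working it through.** No arithmetic applies. The check follows each item the table needs to the field that would supply it.

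**Step 1. A non-bleeding adverse event, without hospitalization, that stops or replaces the drug.**

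| Item needed | Where it would come from | Recorded? |
|---|---|---|
| Sub-population and drug | Baseline form, decision on next therapy | Yes |
| That therapy was stopped or replaced | Follow-up form, codes 4 and 5 | Yes |
| Who decided | Follow-up form, same block | Yes |
| Date | End-of-study form (day may be missing) | Yes |
| Cause | Follow-up therapy block, end-of-study therapy line | No field in either |

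**Step 2. Other routes by which the cause could arrive.** The events block of the follow-up form records bleeding by type and nature, hospitalization with a date and a text entry, and any other event preventing continuation, with a date and a reason. The first two do not apply to the case in step 1, which leaves the other-event line.

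**Step 3. Whether a site is led to that line.** Section 8.3.1 puts interruption of treatment under item c and other events under item d, and the examples for d are surgery and immobilization, not intolerance. The routing note after the therapy block likewise lists newly started, discontinued and changed therapy as items separate from an event preventing continuation. Each goes to the end-of-study form on its own. A site that follows the text would code the stop as a therapy change and finish there.

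**Step 4. Whether a data check closes the gap.** The check on the end-of-study form runs from a ticked other event back to the follow-up form. No check starts from a therapy change, and none links codes 3, 4 or 5 to a reason.

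**Step 5. Therapy newly started (code 3).** The drug boxes that follow the therapy block open only for a replacement (code 5). For an untreated subject in whom therapy is started, neither the drug nor its class has a field. Section 10.4.4 makes this start an endpoint, and 8.3.2 item e promises information on current therapy and its changes. The database could not show whether such subjects moved to an anticoagulant or to an alternative antithrombotic.

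**The case against.** The case for leaving the forms alone has substance. The table is descriptive, with no comparison planned. Adverse drug reactions are left to local pharmacovigilance (8.4) and to local procedures (10.4.5). Bleeding, the main safety outcome, is asked in the same way in all three groups, as are hospitalization and death. Stops remain visible by sub-population under 10.4.4, and only their cause is missing. All of this limits the importance of the point. It does not supply the missing field for a table that the plan promises.

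Five stronger readings may tempt a reader. The documents do not support them.

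- **Such events cannot enter the table.** They can: the other-event line has a reason entry, and the end-of-study form accepts more than one ticked reason. The accurate statement is that entry is optional and unlinked.
- **Treatment-ending events are possible only in the two drug-treated groups.** The synopsis counts interruption of non-pharmacological treatment, and 8.1.1 allows compression in the group without drugs. The imbalance is a matter of degree.
- **The cause is lost for good once the case is closed.** The end-of-study form allows a case to be re-opened by ticket, and 8.5 provides for queries against source documents. Recovery is laborious, not impossible.
- **Section 8.3.2 is contradicted by the form.** Its opening sentence may mean the baseline decision, for which reasons are collected. Item e of the same section lists follow-up changes and who decided them, without a reason. A mismatch is arguable, not shown.
- **The loss can be counted.** With equal thirds of 3,200, the two treated groups hold 3,200 × 2/3 = 2,133 subjects, and an assumed 3% to 10% stopping for an adverse event gives 64 to 213. Equal thirds is only the null hypothesis of section 10.2, and the percentages come from nowhere in the documents. The count also includes stops that would be caught as bleeds, hospitalizations or other events. It is an assumed ceiling, not an estimate.

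**Conclusion.** The point holds in this form. For therapy newly started, stopped or replaced during follow-up, the e-CRF records the type of change, the decider and a date, but no cause. A non-bleeding, non-hospitalized adverse event that stops a drug reaches the table of 10.4.5 and the synopsis only if the site also chooses to complete the other-event line. Under-recording is therefore likely and would fall mainly on the two drug-treated sub-populations. The tabulations of 10.4.4 cannot separate harm from planned completion, choice or cost. Independently of this, the drug started in a previously untreated subject is not recorded.

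The size of the loss cannot be derived from the documents. It depends on how often drugs are stopped for such events and on how often sites use the other-event line unprompted. The conclusion assumes that the e-CRF follows the template in Appendix IV and that the template's therapy block is complete as printed. The primary endpoint is untouched. This is a worthwhile, low-cost improvement to data collection, not a threat to the study.

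**What to change.** 1. In the therapy block of the follow-up form, for codes 3, 4 and 5, add one mandatory coded field for the main reason for change: adverse event or intolerance (specify); bleeding; thrombotic event; new indication or procedure; planned end of therapy; patient choice; cost or availability; other (specify). Dose changes (codes 1 and 2) do not end follow-up and need not trigger it.
2. Open the existing drug boxes for code 3 as well as code 5.
3. In 10.4.5, state that the table is built from this field together with the reason given on the other-event line. Add that drug-stopping events arise essentially in the drug-treated groups, while bleeding, hospitalization and death are asked in the same way in all three.

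The cost is one drop-down, one changed display condition and two sentences in 10.4.5, plus a few seconds of entry per change. The reason will usually be known at the contact, so no visit or procedure is added and no clinical rule changes. For cases already closed, the reason would have to be sought through re-opened forms and source queries.
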